**Randomized Trial of Patient-Reported Outcome Measurement in Heart Failure Clinic
(PRO-HF Trial)**

Version 5

June 30, 2023

CLINICAL TRIAL SUMMARY

Title	Randomized Trial of Patient-Reported Outcome Measurement in Heart Failure Clinic
Study Objectives	
Primary objective is to evaluate the impact of routine assessment of patient-reported health status among outpatients with heart failure on heart failure health status one year later.
 
Secondary objectives include evaluating the following:
 
 - Changes in heart failure therapy patterns - Changes in healthcare utilization (testing, clinic visits, acute care visits) - Patient experience - Concordance between clinician and patient perception of patient health status
Study Design	
This randomized clinical trial evaluates the routine assessment of patient-reported health status, using the Kansas City Cardiomyopathy Questionnaire-12 (KCCQ-12) among adult outpatients with heart failure. Any patients being seen in the heart failure clinics are eligible for enrollment. Patients will be enrolled via secure email or telephone call. They will be randomized in a 1:1 fashion to KCCQ-12 assessment or usual care with permuted block randomization stratified by clinician. Participants randomized to KCCQ-12 assessment will complete the KCCQ-12 at every heart failure clinic visit. Their results will be available to clinicians to assist with clinical management. Health status surveys will not be integrated into clinical care for patients in the usual care arm.
 
In a subset of the total study, we will compare clinician perception of patient health status and patient experience across the two arms.

Number of Participants	Minimum of 1,200 participants will be randomized; 600 patients in sub-study
Trial Location	Stanford Hospital & Clinics adult heart failure clinic
Inclusion Criteria	Adult heart failure clinic visit
Exclusion Criteria	None
Intervention	Participants randomized to KCCQ assessment will complete a KCCQ-12 survey with each heart failure clinic visit. These responses will be shared with their heart failure clinician. Treating clinicians will continue to make all diagnostic and treatment decisions at their discretions.

Primary Endpoint	KCCQ-12 score at least 1 year post-randomization

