Secondary Endpoints	
Treatment patterns at 12 months:
 
 • Rates of guideline-directed therapy use • Dose of guideline-directed medical therapy • Advanced heart failure therapy evaluation • Cardiovascular testing 
Healthcare resource use at 12 months:
 
 • Heart failure clinic visits (in-person and televisits) • Heart failure telephone encounters (other than visits) • Emergency department visits • Hospitalizations (heart failure and non-heart failure)
Other Outcomes of Interest in Sub-Study	
 • Clinician perception of health status • Patient experience
Assessment Schedule	
 • Baseline KCCQ-12 at time of first clinic visit • Repeat KCCQ-12 within 12-15 months post-randomization 
Sub-study:
 
 • Patient experience survey • Clinician evaluation of patient health status
Study Duration	Patients will be enrolled for 12 months. Expected follow-up will be 12-15 months post-randomization. Patients will be followed until their first clinic visit after one year. Patients without a follow-up visit within 15 months, will be contacted for final outcome ascertainment at that time.
Statistical Considerations	A sample size of 1,200 randomized participants has 95% power to detect a mean difference in KCCQ-12 of 5 between arms (72 in KCCQ arm versus 67 in usual care; SD ~24) and an 80% power to detect a mean difference in KCCQ-12 of 4 without covariate adjustment.

TABLE OF CONTENTS

1. LIST OF ABBREVIATIONS AND DEFINITONS	5
2. BACKGROUND AND RATIONALE	6
3. HYPOTHESIS	8
4. STUDY OBJECTIVES	9
5. STUDY DESIGN	10
6. STUDY PROCEDURES	13
7. TREATMENT ARMS	17
8. STUDY ASSESSMENT AND SCHEDULE	18
9. STATISTICAL CONSIDERATIONS AND ANALYSIS PLAN	19
10. DATA HANDLING AND RECORD KEEPING	23
11. DATA AND SAFETY	24
12. PROTOCOL AMENDMENTS	25
13. REFERENCES	26
14. APPENDICES	27

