4. STUDY OBJECTIVES

PRIMARY AIM

The primary aim of this study is to estimate the impact on heart failure health status in 1 year among outpatients with heart failure who are randomized to routine KCCQ-12 assessment vs. usual care.

SECONDARY AIMS

The secondary aims of this trial are to compare the following outcomes at 1 year in participants randomized to KCCQ-12 or usual care:

- Rates of guideline-directed therapy use
- Dose of guideline-directed medical therapy
- Advanced heart failure therapy evaluation
- Cardiovascular testing
- Heart failure clinic visits (in-person and televisits)
- Heart failure telephone encounters (other than visits)
- Emergency department visits
- Hospitalizations (heart failure and non-heart failure)

[figure not shown]
Additional aims include comparing the following outcomes between participants randomized to KCCQ-12 or usual care:

- Patient experience
- Clinician perception of patients' heart failure health status

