Questions 1-4 have ordinal responses with linked questions as described above. For these questions, we will classify concordance as “concordant” if the categories match, “neither concordant or discordant” if the response categories differ by 1, and “discordant” if the response categories differ by >1. For question 5, we will classify as concordant or discordant. We will compare concordance between arms for each of these questions using mixed effects ordinal logistic regression with random intercepts for the treating clinician.

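### The aim of comparing clinician perception between arms is analysed only as agreement with the patient, so the plan cannot show whether clinicians in the KCCQ arm rate patients as sicker or healthier

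*Combined protocol and SAP*

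**What the plan says.** Three places state the aim in terms of perception. In the Clinical Trial Summary, the Study Design entry says "In a subset of the total study, we will compare clinician perception of patient health status and patient experience across the two arms". The summary's list of other sub-study outcomes has "Clinician perception of health status". Section 4 says "Additional aims include comparing the following outcomes between participants randomized to KCCQ-12 or usual care", and one of the two items that follow is "Clinician perception of patients' heart failure health status".

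A fourth place words the topic differently. The secondary objectives in the summary list "Concordance between clinician and patient perception of patient health status".

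Section 9.3.2 is the only place where the clinician survey (Appendix C) is analysed. It has two parts:

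- a linear regression in each arm, giving the share of variation in the KCCQ overall summary score explained by the clinician's NYHA class;
- a concordance category for each question, about which it says "We will compare concordance between arms for each of these questions using mixed effects ordinal logistic regression", with random clinician intercepts. For questions 1-4 the category is a match, a difference of one, or discordant "if the response categories differ by >1". Question 5 is scored as concordant or discordant.

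Section 9.3.1, on the companion outcome of patient experience, compares the score for each question directly between arms.

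**The concern.** The ratings that clinicians give are never compared between arms, and neither is a signed difference between clinician and patient. A clinician who places a patient two classes too well and one who places the patient two classes too badly receive the same concordance category.

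Two readings of the result would then be unsafe. A flat concordance result could be taken to mean that the KCCQ-12 left clinician perception unchanged, although ratings might have moved. An improved result could not say which error was corrected. Direction is of interest because the hypothesis in section 3 concerns changed treatment patterns, and section 9.2 tests whether treatment intensity follows baseline KCCQ-12 more closely in the KCCQ arm. How clinicians' view of severity moved would help to interpret those results.

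**Working it through.** The documents give no effect size, alpha or power for this sub-study, so there is no stated figure to reproduce. The check asks what the two planned analyses can detect.

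**1. Inputs.** From the documents: about 600 sub-study patients (section 6.6) and 1:1 allocation (summary), so about 300 per arm; the category rules in section 9.3.2; the response options in Appendix C. Assumed: two-sided alpha 0.05, no clinician clustering, and all distributions below.

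**2. The concordance category for opposite shifts.** Take 300 patients, 150 in linked class II and 150 in class III (mean 2.5), with clinicians one class off in 30%.

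| Clinician error | Match / off by 1 / off by >1 | Mean class | Mean signed difference |
|---|---|---|---|
| All rated sicker | 70 / 30 / 0% | 2.5 + 0.3 = 2.8 | +0.3 |
| All rated healthier | 70 / 30 / 0% | 2.5 - 0.3 = 2.2 | -0.3 |

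The planned outcome is identical for opposite shifts.

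**3. R-squared.** Adding a constant to a regressor leaves R-squared unchanged. With simulated summary scores (mean 67, SD 24, limited to 0-100), classes from the section 9.3.2 cut-offs and rating noise of one class either way in 20% each, R-squared is 0.607 with no shift, with +1 and with -1. The shifted ratings were not cut off at classes I and IV, so on the real scale the invariance is exact only away from the ends. In the step 2 example, with linked class standing in for the score, the squared correlation is 0.25/(0.25 + 0.30 × 0.70) = 0.25/0.46 = 0.54 in both rows. R-squared therefore does not supply the missing direction.

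**4. How much is lost.** The signed difference is clinician severity minus patient severity, so negative values mean that the clinician rates the patient healthier. The assumed usual-care distribution over -2/-1/0/+1/+2 is 12/28/45/10/5%. Without sign this is 45% match, 28 + 10 = 38% off by one and 12 + 5 = 17% off by two. Power is from a simulated rank test with 300 per arm.

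| Assumed KCCQ arm (-2/-1/0/+1/+2, %) | Unsigned split, % | Power, unsigned | Power, signed |
|---|---|---|---|
| 8.5/19/45/19/8.5 | 45/38/17 | about 5% | 98% |
| 10/23.5/45/14.5/7 | 45/38/17 | about 5% | about 58% |
| Row 1 with match at 55%, other cells × 45/55: 7.0/15.5/55/15.5/7.0 | 55/31/14 | about 64% | 99% |
| 6/20/59/10/5 | 59/30/11 | 94% | about 82% |

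In rows 1 and 2 an ordinal logistic model gave similar results: 4% against 98%, and 7% against 61%. Those rows have the same unsigned split as usual care by construction, so 5% is simply the type I error. They show what the planned model can miss, not what is likely. Repeated runs gave 62-65% for the unsigned test in row 3 and 80-84% for the signed test in row 4.

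**5. What the added analysis could detect.** For a proportional-odds comparison, N = 12(z_a + z_b)² / [(log OR)²(1 - Σp³)]. With 80% power, 12 × (1.960 + 0.842)² = 94.2. For N = 600 and four equal categories, 1 - Σp³ = 1 - 4 × 0.25³ = 0.9375, so log OR = √(94.2/562.5) = 0.409 and OR = 1.51. Over category distributions from uniform to 10/60/25/5%, the detectable odds ratio is 1.51-1.57 with 600 ratings, 1.58-1.66 with 480 and 1.65-1.74 with 400.

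**The case against.** The strongest reply is that concordance is how this plan makes clinician perception measurable. The summary words a secondary objective that way, and section 9.3.2 analyses exactly that objective. This stands. A reader might infer that the aim has no analysis at all; the documents do not support that.

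A reader might also infer that every rating is reduced to an unsigned distance. That goes too far: the NYHA rating also enters the R-squared, and question 5 is nominal, with no sicker or healthier direction to lose.

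Third, a shift that leaves agreement unchanged is unlikely for questions 1-3. The KCCQ-12 is printed for clinicians in the KCCQ arm (section 6.4.3), and the patient category used for scoring comes from the KCCQ-12. Some gain in agreement is to be expected, and the planned test then has power. If the only change is less under-rating, it is the better test. So one cannot say that the planned model would report no effect. Nor do the documents state that the intervention works by revealing burden that clinicians had missed; that is a plausible mechanism, not a stated one.

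Fourth, these are additional aims without a power statement, and no primary or secondary endpoint is biased. This is true and limits the weight of the point. It does not close the gap: as worded in three places, the aim is to compare perception, and no planned output gives its direction.

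**Conclusion.** The point holds in limited form. The concordance objective is analysed. The perception aim is analysed only through agreement, and neither planned analysis can tell a shift towards sicker ratings from one towards healthier ratings, or say which kind of error an improvement removed. This follows from the category rules and needs no assumption.

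The cost in power does rest on assumptions. It runs from total, when the unsigned split is unchanged, through moderate when agreement also rises, to none when only under-rating falls. Clinician clustering and non-response are not in these figures. The primary result is unaffected.

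**What to change.** Keep the concordance score as the analysis of the concordance objective. In section 9.3.2 add, labelled exploratory:

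- (a) a between-arm comparison of each clinician rating in questions 1-4, with each question 3 symptom separate, using the same mixed effects ordinal logistic model and random clinician intercept. Exclude don't-know answers and report their frequency by arm, since that exclusion follows randomization;
- (b) by arm, the proportions rated sicker than, the same as, and healthier than the linked patient category, with the same model on the signed difference. The linked category rests on cut-offs that the plan itself treats as approximate, so describe the result as relative to the patient category, not as clinician error.

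For fatigue and shortness of breath, (b) must wait until the mapping in section 9.3.2 is reconciled with Appendix C. For these two symptoms Appendix C merges no episode and one episode into a single option and adds a top option above daily, whereas the mapping separates none from once and stops at daily. Part (a) does not need the mapping.

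State that conclusions about clinician perception rest on (a) and (b), and conclusions about agreement on the concordance score.

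The data are already collected in Appendix C. The cost is SAP wording and about 14 exploratory tests (seven items: questions 1, 2 and 4 and four symptoms; 7 × 2 = 14) beside the eight planned concordance comparisons. If these are not added, reword the aim in the summary and section 4 as concordance only.

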10. DATA HANDLING AND RECORD KEEPING

10.1 Electronic Data Capture (EDC) System

EHR data will be extracted via the STARR registry and kept on the REDCap system. After data extraction, patients will be de-identified and labeled with a study ID number. Linkage between the medical record number and study ID will be kept separately as a locked file and only be available to the data analyst.

10.2 Data Confidentiality and Security

Computerized data will be accessible only by password. The Stanford University computer network is protected by a firewall. Participants will be identified by study number only, to ensure participant anonymity. No participant identifiers will be used in the presentation of data. Study records that might identify participants will be kept confidential as required by law. Except when required by law, participants will not be identified by name, personal identification number (e.g. social security number, social insurance number), address, telephone number, or any other direct personal identifier in study records.

10.3 Training

All investigational site staff authorized to enter the study data will receive training on the EDC system.

10.4 Records Retention

Study records will be maintained by the site investigators for a period of six (6) years following the expiration of the grant or length of time as required by local regulations, whichever is longer.

11. DATA AND SAFETY

11.1 OVERALL PLAN

As per NHLBI requirements, there is a data and safety monitoring plan commensurate with the risk of the trial. The planned study is minimal risk and non-blinded given the intervention solely consists on an additional patient survey of health status at the time of clinic visits. The heart failure clinician will continue to make all treatment decisions.

The data and safety monitoring plan will screen for any concerns, unanticipated problems, or adverse events related to KCCQ assessment. Both heart failure clinic staff and enrolled patients will be given contact information for the study team to report concerns related to assessment.

The independent safety monitors will be [name], Assistant Professor (Cardiovascular Medicine) at University of Colorado and [name] at Swedish Hospital in Seattle, Washington. [name] is an advanced heart failure specialist. She is also a health services researcher with experience evaluating heart failure health status. [name] is also an advanced heart failure specialist with experience in clinical research. He also has detailed experience with the Stanford cardiology clinics, having completed his cardiology fellowship at Stanford. They will review issues raised by clinic staff or heart failure patients as they arise and will advise the research study team regarding the need to adjust the collection protocol or terminate the study prematurely.

Adverse events or serious adverse events related to KCCQ assessment are very unlikely. Potential adverse events detected by heart failure clinic staff or patients will be reported to the study principal investigator on a continuous basis. Potential adverse events will also be reported to the Stanford University IRB committee and the NIH Program Officer. As a second step, the PI, IRB committees, and the independent safety monitors will review adverse events to evaluate if the events were caused by the intervention.

12. PROTOCOL AMENDMENTS

12.1 Protocol Amendments

Any change or addition to the protocol can only be made in a written protocol amendment that must be approved by the IRB. Notwithstanding the need for approval of formal protocol amendments, the investigator is expected to take any immediate action required for the safety of any participant included in this study, even if this action represents a deviation from the protocol. In such cases, the IRB will be informed.

Appendix A: Kansas City Cardiomyopathy Questionnaire-12

Kansas City Cardiomyopathy Questionnaire (KCCQ-12)

The following questions refer to your **heart failure** and how it may affect your life. Please read and complete the following questions. There are no right or wrong answers. Please mark the answer that best applies to you.

1. **Heart failure** affects different people in different ways. Some feel shortness of breath while others feel fatigue. Please indicate how much you are limited by **heart failure** (shortness of breath or fatigue) in your ability to do the following activities over the past 2 weeks.

Activity	Extremely Limited	Quite a bit Limited	Moderately Limited	Slightly Limited	Not at all Limited	Limited for other reasons or did not do the activity
a. Showering/bathing						
b. Walking 1 block on level ground						
c. Hurrying or jogging (as if to catch a bus)						

2. Over the past 2 weeks, how many times did you have **swelling** in your feet, ankles or legs when you woke up in the morning?

Every morning	3 or more times per week but not every day	1-2 times per week	Less than once a week	Never over the past 2 weeks
				

3. Over the past 2 weeks, on average, how many times has **fatigue** limited your ability to do what you wanted?

All of the time	Several times per day	At least once a day	3 or more times per week but not every day	1-2 times per week	Less than once a week	Never over the past 2 weeks
						

4. Over the past 2 weeks, on average, how many times has **shortness of breath** limited your ability to do what you wanted?

All of the time	Several times per day	At least once a day	3 or more times per week but not every day	1-2 times per week	Less than once a week	Never over the past 2 weeks
						

5. Over the past 2 weeks, on average, how many times have you been forced to sleep sitting up in a chair or with at least 3 pillows to prop you up because of **shortness of breath**?

Every night	3 or more times per week but not every day	1-2 times per week	Less than once a week	Never over the past 2 weeks
				

6. Over the past 2 weeks, how much has your **heart failure** limited your enjoyment of life?

It has extremely limited my enjoyment of life	It has limited my enjoyment of life quite a bit	It has moderately limited my enjoyment of life	It has slightly limited my enjoyment of life	It has not limited my enjoyment of life at all
				
1	2	3	4	5

7. If you had to spend the rest of your life with your **heart failure** the way it is right now, how would you feel about this?

Not at all satisfied	Mostly dissatisfied	Somewhat satisfied	Mostly satisfied	Completely satisfied
				
1	2	3	4	5

8. How much does your **heart failure** affect your lifestyle? Please indicate how your **heart failure** may have limited your participation in the following activities over the past 2 weeks.

Activity	Severely Limited	Limited quite a bit	Moderately limited	Slightly limited	Did not limit at all	Does not apply or did not do for other reasons
a. Hobbies, recreational activities						
b. Working or doing household chores						
c. Visiting family or friends out of your home						
	1	2	3	4	5	6

Appendix B: Clinic Experience Survey

This survey is to evaluate your experience at your recent cardiology clinic visit. Using the 5-item scale below each question, please indicate how much you agree with the following statements by **marking the answer that best applies** to you :

1.) My clinician **listened to me** carefully:

 Completely agree	 Somewhat agree	 Neither agree nor disagree	 Somewhat disagree	 Completely disagree
--	--------------------------------------	--	---	---

2.) My clinician **understood symptoms** related to my heart:

 Completely agree	 Somewhat agree	 Neither agree nor disagree	 Somewhat disagree	 Completely disagree
--	--------------------------------------	--	---	---

3.) My clinician **showed respect** for what I had to say:

 Completely agree	 Somewhat agree	 Neither agree nor disagree	 Somewhat disagree	 Completely disagree
--	--------------------------------------	--	---	---

4.) My clinician and I **agreed on how I was doing overall**:

 Completely agree	 Somewhat agree	 Neither agree nor disagree	 Somewhat disagree	 Completely disagree
--	--------------------------------------	--	---	---

5.) My clinician **spent enough time** with me:

 Completely agree	 Somewhat agree	 Neither agree nor disagree	 Somewhat disagree	 Completely disagree
--	--------------------------------------	--	---	---

6.) My clinician explained things in a way that was easy to understand:

 Completely agree	 Somewhat agree	 Neither agree nor disagree	 Somewhat disagree	 Completely disagree
--	--------------------------------------	--	---	---

7.) I understand the **importance of taking the treatments** recommended by my clinician:

 Completely agree	 Somewhat agree	 Neither agree nor disagree	 Somewhat disagree	 Completely disagree
--	--------------------------------------	--	---	---

8.) My goals regarding treatment and those of my clinician are aligned:

 Completely agree	 Somewhat agree	 Neither agree nor disagree	 Somewhat disagree	 Completely disagree
--	--------------------------------------	--	---	---

9.) What has the biggest impact on your quality of life?

 Heart Failure	 Other Cardiovascular Problems	 Other Medical Problems	 Heart Failure and Other Medical Problems	 Non-medical Reasons	 None of the Above
			Equally		

10.) In terms of your overall quality of life, how do you expect your heart failure health status to change over the following year:

 Significant Improvement	 Mild Improvement	 Remain Stable	 Mild Worsening	 Significant Worsening
---	--	-------------------------------------	--------------------------------------	---

